6.13. Pharmacokinetic/Pharmacodynamic Analyses

LY3154207 plasma concentrations will be illustrated graphically and summarized descriptively. Subject data, including but not limited to plasma LY3154207 concentrations, from other clinical studies evaluating LY3154207 may be combined with data from this study to support additional analyses.

If warranted and based on availability of data, the exposure-response relationship of plasma LY3154207 concentrations to efficacy endpoints and/or safety endpoints may be explored.

6.14. Safety Analyses

All subjects who receive at least 1 dose of double-blind study treatment will be evaluated for safety and toxicity.

Safety parameters (AEs, laboratory tests, vital signs, electrocardiograms [ECGs], and discontinuation rates) for meeting Day 1 (Visit 3) stopping rules will be summarized for the treatment period using descriptive statistics for continuous variables and frequencies and percentages for categorical variables.

Comparisons between the 3 LY3154207 doses and placebo will be made using a frequentist MMRM model for the in-clinic BP, PR, and HBPM measurements during the treatment period.

6.14.1. Extent of Exposure

Days of exposure will be calculated for all subjects as the (Date of last dose – date of first dose + 1). Summary statistics will be presented for the total number of days of exposure by treatment.

Cumulative exposure will be calculated for each subject and will be summarized with descriptive statistics by treatment arm.

A listing of drug accountability by subject will be created and the reason for any drug interruptions given.

6.14.2. Adverse Events and Serious Adverse Events

Treatment-emergent AEs will be defined as events that first occurred or worsened on or after randomization (Visit 3). Should there be insufficient data to determine whether an AE is treatment emergent, the AE will be considered treatment emergent.

Treatment-emergent AEs will be calculated based on adverse event identifier (AEID) and coded according to established Medical Dictionary for Regulatory Activities (MedDRA) terms and summarized by MedDRA System Organ Class (SOC) and Preferred Term. Adverse event terms and severity grades will be assigned by the investigator using Common Terminology Criteria for Adverse Events (CTCAE) version 4.0.

An overview of AEs, including the number and percentage of subjects who died, suffered serious AEs (SAEs), discontinued due to AEs, and who suffered treatment-emergent AEs (TEAEs), will be provided.

Summaries of AEs by decreasing frequency of Preferred Term within SOC will be provided for the following:

- preexisting conditions (medical history)
- TEAEs
- TEAEs by maximum severity
- TEAEs occurring in greater than 1% of subjects by Preferred Term
- SAEs, and
- AEs reported as reason for discontinuation.

These summaries will include number and percentages of subjects with TEAEs.

A summary of TEAEs by visit will also be provided.

SAEs and discontinuations due to AEs will be listed.

An SAE is any AE from this study that results in 1 of the following outcomes:

- death
- initial or prolonged inpatient hospitalization
- a life-threatening experience (i.e. immediate risk of dying)
- persistent or significant disability/incapacity
- congenital anomaly/birth defect
- important medical events that may not be immediately life-threatening or result in death or hospitalization but may jeopardize the subject or may require intervention to prevent 1 of the other outcomes listed in the definition above. Examples of such medical events include allergic bronchospasm requiring intensive treatment in an emergency room or at home, blood dyscrasias or convulsions that do not result in inpatient hospitalization, or the development of drug dependency or drug abuse.

6.14.3. Deaths, Other Serious Adverse Events, and Other Notable Adverse Events

Any deaths will be listed and summarized.

Separate summaries by treatment group will be produced for any major cardiovascular TEAEs (including congestive heart failure, hypertension, myocardial infarction, stroke, and tachycardia) and major nervous system disorders TEAEs (including dyskinesias, impulse control disorders, delirium, confusion, and psychosis).

6.14.4. Clinical Laboratory Evaluation

Laboratory measures (clinical chemistry, hematology, and urinalysis) will be analyzed as continuous data (change from baseline) measured as International System of Units (SI) or as

categorical data (proportion of treatment-emergent abnormalities). If there are multiple records of laboratory measurements at baseline or postbaseline visits, the last record will be used.

Change from baseline to postbaseline visits at which laboratory measurements are taken will be summarized using descriptive statistics. A listing of abnormal laboratory data will be produced.

For all laboratory tests, frequencies of subjects with notable changes (that is, increases or decreases of a prespecified amount unique to each analyte) from baseline to each postbaseline visit will also be summarized for all subjects and stratified by low, normal, or high at baseline.

6.14.5. Vital Signs and Other Physical Findings

Vital Signs

Vital sign measurements and weight will be analyzed as continuous data (change from baseline) and the treatment-emergent abnormalities as categorical data.

If there are multiple records of vital sign or weight measurements at baseline or a postbaseline visit, the last record will be used. The only exception is for orthostatic BP and PR taken at Visit 1, Visit 4, Visit 5, Visit 6, Visit 7, Visit 9, Visit 10, unscheduled visit, and early termination/discontinuation visit and the initial measurement at time 0 of the in-clinic BP and PR monitoring. At these visits, 3 seated BP/PR measurements will be taken and the mean of these will be utilized for analysis purposes. Orthostatic changes will be calculated by comparing the mean of the 3 seated BP and PR values to the single standing BP and PR values.

The incidence of treatment-emergent abnormal high or low vital signs will be presented by treatment group and visit. Treatment-emergent vital sign evaluations are defined for evaluations collected after the initiation of study medication. Any vital sign meeting the criteria will be considered abnormal. For each vital sign at each postbaseline visit, only subjects who had a baseline result and had a non-missing result at that postbaseline visit will be included in the denominator when computing the proportion of subjects with treatment-emergent high, low, or abnormal values. Criteria for abnormal postbaseline vital signs are presented in [Appendix 1](#).

The following will be summarized by treatment group and visit for all subjects in the Safety population: SBP, DBP, and PR (collected in sitting position); orthostatic SBP, orthostatic DBP, and orthostatic PR (measurement after 5 minutes in the seated position minus that after 3 minutes in the standing position); temperature; and weight. Body mass index at baseline will be summarized by treatment. Summary statistics will be presented for observed values at baseline and for change from baseline results at each scheduled postbaseline visit.

A listing of treatment-emergent abnormal vital signs by subject and visit will also be presented.

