- g In-clinic BP and pulse rate monitoring will be done at Visit 2, Visit 3, Visit 8, Visit 11, and Visit 801. The BP and pulse rate measurements will occur at time 0 and approximately every 60 minutes thereafter at Visit 2, Visit 8, and Visit 11, in-clinic BP and pulse rate will be monitored for up to 6 hours; at Visit 3, for up to 8 hours and at Visit 801 for up to 2 hours.. The initial measurement, time 0 of the in-clinic BP and pulse rate monitoring, will be done as an orthostatic BP/pulse rate (refer to footnote f above), and subsequent BP and pulse rate measurements will be done in the seated position only. Time 0 for Visit 3, Visit 8, and Visit 11 will occur just prior to study drug dosing. At Visit 3, drug dosing should be initiated immediately following confirmation that subject meets inclusion criteria [6].
- h The subject should be given the HBPM device at Visit 2. Home BP will be measured twice daily in the seated position using the HBPM equipment provided by Eli Lilly and Company (Lilly). Home BP measurements should be conducted for a minimum of 7 days between Visit 2 and Visit 3, for 3 weeks between Visit 3 and Visit 6, and for a minimum of 7 days between Visit 10 and Visit 11, and Visit 11 and Visit 801. Home BP should be measured twice in the morning (approximately 1 minute apart) (e.g., 8 AM) immediately following study medication dosing and twice in the evening, approximately 12 hours later (approximately 1 minute apart) (e.g., 8 PM).
- i Refer to inclusion criterion [12e] in Section 6.1.
- j PK sampling. At Visit 3, a PK sample is to be collected within 1 to 3 hours after the drug is administered at the site. At Visit 4, Visit 5, Visit 8, and ET/DC visit, the PK sample can be collected at any time during the visit. At Visit 11, the PK sample should be collected prior to the drug being administered at the site. The date and time of the PK sample collection as well as the date and time of the dose administration immediately preceding the PK sampling should be entered in the eCRF.
- k Study drug dose to be administered at the clinic on the morning of Visit 8 and Visit 11 following the Time 0 in-clinic BP/pulse rate measurements.

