8.1. Discontinuation from Study Treatment

8.1.1. *Permanent Discontinuation from Study Treatment*

Possible reasons leading to permanent discontinuation of study treatment:

- Subject Decision
 - the subject or the subject's designee, for example, legal guardian, requests to discontinue the investigational product.
- Day 1 stopping rules - Discontinuation due to change in acute vital signs on Day 1 (Visit 3)

If during Day 1 (Visit 3) and following study drug dosing, any of the potentially clinically significant vital signs criteria ([Table HBEH.3](#)) are met at 3 *consecutive* time points using in-clinic vital sign monitoring, then the subject should be discontinued from the study drug. The relative value of the potentially clinically significant vital sign criteria is calculated by comparing to the mean of the 3 seated blood pressure and pulse rate at Time 0 of Visit 3 (baseline).

- For vital sign measurements that meet the criteria for potentially clinically significant vital signs ([Table HBEH.3](#)) after Visit 3, management will be left to the discretion of the investigator and may include discontinuation of study drug. The investigator should consult with the Lilly CRP or designee.
- Discontinuation due to a hepatic event or liver test abnormality
Subjects who are discontinued from the study due to a hepatic event or liver test abnormality should have additional hepatic safety data collected via eCRF. Discontinuation of the investigational product for abnormal liver tests should be considered by the investigator when a subject meets 1 of the following conditions after consultation with the Lilly-designated medical monitor:
 - ALT or AST >8X ULN
 - ALT or AST >5X ULN for more than 2 weeks
 - ALT or AST >3X ULN and TBL >2X ULN or international normalized ratio >1.5
 - ALT or AST >3X ULN with the appearance of fatigue, nausea, vomiting, right upper-quadrant pain or tenderness, fever, rash, and/or eosinophilia (>5%)
 - ALP >3X ULN
 - ALP >2.5X ULN and TBL >2X ULN
 - ALP >2.5X ULN with the appearance of fatigue, nausea, vomiting, right quadrant pain or tenderness, fever, rash, and/or eosinophilia (>5%)

In addition, subjects will be discontinued from the investigational product in the following circumstances:

- Mean Fredericia's corrected QT interval on the ECG (QTcF) >500 milliseconds or an absolute change >60 milliseconds when compared with baseline

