9.4.2. Vital Signs

Vital signs including pulse rate, orthostatic BP, temperature, and weight will be measured as detailed in the Schedule of Activities (Section 2).

Orthostatic Blood Pressure Monitoring: For orthostatic BP monitoring, subjects will have 3 BP/pulse rate measurements taken in the seated position approximately 1 minute apart followed by 1 BP/pulse rate measurement taken in the standing position. For orthostatic BP monitoring, subjects should be seated for at least 5 minutes and stand for at least 3 minutes prior to taking the respective measurements. If the subject feels unable to stand, vital signs only in the seated position will be recorded.

Orthostatic BP/pulse rate will be measured as part of the vital sign assessments at every visit. At Visit 2, Visit 3, Visit 8, Visit 11, and Visit 801, these measurements will be collected at time 0 of the in-clinic BP/pulse rate monitoring. Unscheduled orthostatic vital signs should be assessed, if possible, during any AE of dizziness or posture-induced symptoms. Additional vital signs may be measured during each study period if warranted and agreed upon between the sponsor and investigator. (Table HBEH.3)

In-clinic Blood Pressure and Pulse Rate Monitoring: In-clinic BP and pulse rate monitoring will be done at Visit 2, Visit 3, Visit 8, Visit 11, and Visit 801. The BP and pulse rate will be measured at time 0 and every 60 minutes thereafter. The initial measurement, at time 0 of the in-clinic BP and pulse rate monitoring, will be done as an orthostatic BP/pulse rate (refer to Orthostatic Blood Pressure Monitoring above), and subsequent BP and pulse rate measurements will be taken in the seated position only. Time 0 at Visit 3, Visit 8 and Visit 11 will occur just prior to study drug dosing. At Visit 3, drug dosing should be initiated immediately following confirmation that subject met inclusion criteria [6]. At Visit 2, Visit 8, and Visit 11, in-clinic BP and pulse rate will be monitored for up to 6 hours, At Visit 3, for up to 8 hours and at Visit 801 for up to 2 hours (Table HBEH.4).

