Home Blood Pressure Monitoring: Home BP measurements will be collected in this study. Blood pressure measurements should be taken twice daily in the seated position using the HBPM equipment provided by Lilly. The subject should be given the HBPM device at Visit 2. Home BP measurements should be conducted for a minimum of 7 days between Visits 2 and 3, for 3 weeks between Visits 3 and 6, and a minimum of 7 days between Visits 10 and 11, and Visits 11 and 801. Home BP should be taken twice in the morning (approximately 1 minute apart) (e.g., 8 AM) immediately following study medication dosing and twice in the evening, approximately 12 hours later (approximately 1 minute apart) (e.g., 8 PM).

All HBPM data will be electronically transmitted to a designated HBPM data processing vendor.

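### Read literally, the SAP's last-record rule leaves one hourly reading per visit in the vital-sign abnormality table; separately, the Appendix 1 orthostatic rows use an unmeasured posture and no baseline condition

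*SAP*

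**What the plan says.** **Record rule.** SAP 6.14.5 states: "If there are multiple records of vital sign or weight measurements at baseline or a postbaseline visit, the last record will be used". It names a single exception: the triplicate seated sets taken with the orthostatic measurements, and the time-0 measurement that opens in-clinic monitoring. These are averaged. Hours 1 onward are not exempted. Protocol 10.3.4.3 carries the same rule.

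**Abnormality table.** The same SAP section then calls for the incidence of high and low values by treatment and visit, plus a listing, judged against Appendix 1. It adds "Any vital sign meeting the criteria will be considered abnormal". It defines the post-dose scope by timing: "Treatment-emergent vital sign evaluations are defined for evaluations collected after the initiation of study medication". The denominator requires that a baseline result exists, not that it was normal.

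**Schedule.** Protocol 9.4.2 has hourly blood pressure and pulse at Visits 2, 8 and 11 "monitored for up to 6 hours, At Visit 3, for up to 8 hours and at Visit 801 for up to 2 hours". Footnote g of the Schedule of Activities adds: "Time 0 for Visit 3, Visit 8, and Visit 11 will occur just prior to study drug dosing".

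**Orthostatic values.** Protocol 9.4.2 takes three seated readings and then one standing reading. SAP 6.14.5 matches this: "Orthostatic changes will be calculated by comparing the mean of the 3 seated BP and PR values" with the single standing value. All three orthostatic rows of SAP Appendix 1 are instead defined from five minutes supine to three minutes standing. The Appendix 1 rows for systolic pressure, diastolic pressure and pulse pair an absolute limit with a change from baseline. The orthostatic rows have no baseline term.

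**The concern.** The by-visit table and listing are where a reader would look for individual values that cross the Appendix 1 limits. A one-value-per-visit rule is sensible for a scale score or a single seated reading. Applied to a post-dose series, it can remove the hours in which an acute effect on pressure or pulse would show. Acute and 12-week effects on blood pressure and pulse are secondary safety objectives. Protocol 8.1.1 also refers to individual crossings after Visit 3 ("For vital sign measurements that meet the criteria for potentially clinically significant vital signs"), so the same criteria matter at visits where the table may see only one reading.

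For the orthostatic rows, the stated posture cannot be programmed from the data collected. In addition, the label treatment-emergent would attach to drops that the subject already had before the first dose.

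**Working it through.** The plan states no figure for this table, so the check is a count of scheduled readings followed by a comparison of the texts.

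**1. Scheduled post-dose hourly readings** (Protocol 9.4.2 and 5.1.3.1; Schedule of Activities footnote g):
- Visit 3: hours 1 to 8 = 8
- Visit 8: hours 1 to 6 = 6
- Visit 11: hours 1 to 6 = 6
- Total: 8 + 6 + 6 = 20

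**2. Readings that reach the table, by how the rule is read:**

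| Reading of the rule | Visits 3, 8, 11 | Visits 8, 11 only |
|---|---|---|
| Last hourly value of the visit | 3 of 20 (3/20 = 15%) | 2 of 12 |
| Time-0 mean stands for the visit | 0 of 20 | 0 of 12 |
| Last of duplicate records at one time point | 20 of 20 | 12 of 12 |

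The first two rows follow from treating the visit as the unit, which is how the sentence is worded. The second fails at Visit 3 on the SAP's own terms, because time 0 there precedes the first dose. At Visits 8 and 11 a time-0 value is on treatment but precedes that day's dose. The third row needs a limitation that the text does not state.

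**3. Consistency with the Day 1 stopping rule.** A run of exactly three consecutive abnormal readings within hours 1 to 8 can start at hours 1 to 6, giving 6 positions. Only the run at hours 6, 7 and 8 includes the last reading. In the other 5 positions a subject meets the Day 1 criterion yet is missing from the Visit 3 row if the last hourly value is used. This assumes a complete 8-hour series and counts positions, not probabilities. If monitoring ended once the rule was met, the last record would probably be abnormal and be captured.

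**4. Whether other analyses count the same crossings:**
- Day 1: the stopping-rule count draws on the hourly series, and the Day 1 MMRM (SAP 6.14.7.1) uses every hour. Visit 3 is largely covered.
- Visits 8 and 11: the MMRM response is a 0 to 6 hour average, which does not count crossings.
- Home readings are taken "immediately following study medication dosing and twice in the evening, approximately 12 hours later", so none is scheduled 1 to 6 hours after dosing. None is scheduled between Visits 6 and 10, which includes Visit 8.
- Ambulatory monitoring (SAP 6.14.7.4) covers addendum participants only and is analysed as averages, nocturnal dip and graphs.
- Adverse-event summaries do not apply the Appendix 1 limits.

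**5. Orthostatic rows.** Measured: seated to standing (Protocol 9.4.2). Calculated: seated to standing (SAP 6.14.5). Judged: supine to standing (Appendix 1). The protocol asks for supine rest only before ECGs. On baseline status, Appendix 1 has no condition for these rows and SAP 6.14.5 defines treatment-emergent by timing alone, so a drop seen before dosing and again afterwards is counted. A pre-dose set exists at Visit 3 time 0 (Protocol 5.1.3.1), so the condition could be applied.

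**The case against.** The strongest reply is that this is a wording gap with little at stake. The exception is written partly at time-point level. The sentence "Any vital sign meeting the criteria will be considered abnormal" sits in the abnormality paragraph itself. The hourly series has its own analysis section. Using one value per visit is also a convention elsewhere in the SAP, for example for laboratory data. Protocol 8.1.1 leaves crossings after Visit 3 to the investigator's judgement and does not ask for a table of every reading. For orthostatic values the operative calculation is stated and no supine pressure exists, so a programmer has only one option; by-visit changes from baseline are summarised as well.

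Much of this stands. The any-reading sentence may show intent, but it does not say which records remain eligible once the last-record rule has been applied. Mean orthostatic changes would show a shift, but they do not separate new drops from old ones.

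Three stronger inferences are not supported:
- **That the plan discards its hourly safety data.** The Day 1 series and the 0 to 6 hour averages are analysed.
- **That using 15% of readings means missing 85% of events.** A share of readings is not a share of affected subjects.
- **That the ECG section sets an any-reading precedent.** It also reduces each visit to one averaged record before counting subjects with at least one qualifying value.

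**Conclusion.** The point holds in limited form. As worded, the record rule leaves one value per visit from the hourly series in the abnormality table and listing: 3 of 20 post-dose readings at Visits 3, 8 and 11 if the last hourly value is taken, and 2 of 12 at Visits 8 and 11. The practical gap is individual exceedances at Visits 8 and 11. The documents give no rates from which the number missed could be derived. The count assumes a full monitoring schedule in a subject who completes treatment.

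The orthostatic rows contradict the measurement procedure and label some pre-existing drops as treatment-emergent. A reader might infer that this distorts the comparison with placebo. It does not: the same definition applies in every randomised arm, so it adds noise and mislabels events without favouring an arm.

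**What to change.** (a) Limit the last-record rule to repeat records of the same time point. For the incidence table and listing, count a subject as abnormal at Visits 3, 8 and 11 if any scheduled post-dose reading meets Appendix 1. If the prespecified table is kept, add this as a supplementary count. State which value feeds the by-visit descriptive summaries.

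(b) Count an orthostatic abnormality as treatment-emergent only if it was absent at the pre-dose baseline.

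(c) Have the sponsor reconcile the posture in Appendix 1 with SAP 6.14.5 and Protocol 9.4.2 and confirm the criterion that applies.

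The cost is SAP wording and programming on data already collected. Any-reading counts will rise in every arm, including placebo, and must be read against placebo. The SAP revision history says Version 3 was approved after unblinding, so the change should be labelled post hoc and explained in the clinical study report.

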6.14.6. Electrocardiograms

The ECG measurements will be analyzed as continuous data (change from baseline) or as categorical data (proportion of treatment-emergent abnormalities).

Electrocardiogram is measured in triplicate during the double-blind period, and the average of triplicates will be used at baseline and each double-blind period visit. If there are multiple records after averaging ECG triplicates within a visit, the last record of averages will be used.

All ECG parameter changes from baseline to each postbaseline visit at which ECG measurements are taken will be summarized. All analyses of QTc will be carried out using the Fridericia's correction (QTcF) method.

Incidence of treatment-emergent abnormal ECGs will be also be summarized. For example, the frequency of subjects with abnormal treatment-emergent increases from baseline in QTcF intervals will be summarized into the following categories: >30 msec and >60 msec.

Treatment-emergent elevated QTc intervals will be summarized into the following categories: >450 msec, >480 msec, and >500 msec. Baseline is the average of the last set of triplicates measured prior to taking study drug. Each category will show the number of subjects who have at least 1 treatment-emergent value meeting that criteria, and therefore those meeting the top criteria of >60 and >500 with be counted in lower categories as well.

